8.3.3. Assessment OF RELATEDNESS OF AE OR SAE TO STUDY DRUGS

The investigator is obligated to assess the relationship between study drug and the occurrence of each AE/SAE using the following categories of relatedness:

- Definite: clear-cut temporal association

- Probable: clear-cut temporal association, with improvement upon drug withdrawal, and not reasonably explained by the patient's known clinical state or other aetiology.
- Possible: less clear temporal association; other aetiologies are possible. (Other possible aetiologies should be recorded on the CRF).
- Not related: no temporal association with the study drug; assessed as related to other aetiologies such as concomitant medications or conditions, or patient's known clinical state.

The investigator will provide the assessment of causality as per the AE/SAE case record form.

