The most important reported side effect of artesunate is a rare severe allergic reaction (estimated risk approximately 1 in 3000 patients), which can present as an urticarial rash or more severe allergic symptoms, including hypotension, pruritus, oedema, and/or dyspnoea. More common minor side effects described in association with parenteral administration of artesunate include dizziness, light-headedness, rash, and taste alteration (metallic/ bitter taste). Nausea, vomiting, anorexia and diarrhoea have also been reported, however it is uncertain whether these are attributable to the drug or to the disease severe malaria.

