Safety data will be presented in tabular and/or graphical format and summarized descriptively. Any clinically relevant abnormalities or values of potential clinically concern will be described. Patients will be analysed following the intention to treat analysis. All adverse event summaries will refer to treatment emergent adverse events, i.e. adverse events that newly started or increased in intensity after the study drug administration. Adverse events will be graded according to Common Terminology Criteria for Adverse Events (CTCAE). The safety and tolerability summaries will be presented in table 5.

Table 5 Incidence of adverse events within first 28 days by study arm

	1-STEP AS	2-STEP AS	p-value
Number of subjects	XX	XX	
Serious adverse events (SAEs), n/N, (%)	XX	XX	X.XXX
Possible, probable or definite drug related SAEs, n/N, (%)	X/XX (X.X)	X/XX (X.X)	X.XXX
Neurological sequelae at discharge	X/XX (X.X)	X/XX (X.X)	X.XXX
Neurological sequelae at 28	X/XX (X.X)	X/XX (X.X)	X.XXX
Neurological sequelae persisting at end of follow up	X/XX (X.X)	X/XX (X.X)	X.XXX
Grading of adverse events, n/N, (%)	1-2	3-4	1-2
Symptoms			
Impaired consciousness or unrousable coma, n (%)	X/XX (X.X)	X/XX (X.X)	X/XX (X.X)
Prostration, n (%)	X/XX (X.X)	X/XX (X.X)	X/XX (X.X)
Failure to feed and drink without assistance, n (%)			
Multiple convulsions, n (%)			
Deep breathing, respiratory distress, n (%)	X/XX (X.X)	X/XX (X.X)	X/XX (X.X)
Circulatory collapse or shock, systolic BP < 70 mmHg, n (%)	X/XX (X.X)	X/XX (X.X)	X/XX (X.X)
Clinical jaundice plus evidence of other vital organ dysfunction, n (%)	X/XX (X.X)	X/XX (X.X)	X/XX (X.X)
Haemoglobinuria, n (%)	X/XX (X.X)	X/XX (X.X)	X/XX (X.X)
Suspected pulmonary oedema, n (%)	X/XX (X.X)	X/XX (X.X)	X/XX (X.X)

STATISTICAL ANALYSIS PLAN

	X/XX (X.X)	X/XX (X.X)	X/XX (X.X)	X/XX (X.X)	X.XXX
Renal failure (< 20 ml urine per hour) , n (%)	X/XX (X.X)	X/XX (X.X)	X/XX (X.X)	X/XX (X.X)	X.XXX
Spontaneous bleeding/disseminated intravascular coagulation, n (%)	X/XX (X.X)	X/XX (X.X)	X/XX (X.X)	X/XX (X.X)	X.XXX
Several episodes of vomiting in the preceding 24 hrs, n (%)	X/XX (X.X)	X/XX (X.X)	X/XX (X.X)	X/XX (X.X)	X.XXX
Severe pallor with respiratory distress OR HCT<15% OR hb<5.0g/dl, n (%)	X/XX (X.X)	X/XX (X.X)	X/XX (X.X)	X/XX (X.X)	X.XXX
Total	X/XX (X.X)	X/XX (X.X)	X/XX (X.X)	X/XX (X.X)	X.XXX
Laboratory abnormalities					
Creatinine	X/XX (X.X)	X/XX (X.X)	X/XX (X.X)	X/XX (X.X)	X.XXX
Total bilirubin	X/XX (X.X)	X/XX (X.X)	X/XX (X.X)	X/XX (X.X)	X.XXX

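### The causality scale in Protocol 8.3.3 is out of order, and a malaria-driven serious event soon after an injection can be rated drug related

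*Protocol*

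**What the plan says.** Protocol 8.3.3 asks the investigator to rate every AE and SAE on four levels.

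- Top level: "Definite: clear-cut temporal association". No other condition is given.
- Probable: the same clear timing, "with improvement upon drug withdrawal, and not reasonably explained by the patient's known clinical state or other aetiology".
- The third level down reads "Possible: less clear temporal association; other aetiologies are possible".
- The bottom level reads "Not related: no temporal association with the study drug; assessed as related to other aetiologies". The sentence goes on to name concomitant treatment or conditions and the patient's known clinical state.

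Three other places decide which events reach this scale and how the rating is used.

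- Protocol 8.1.1 lists 13 common complications of deteriorating severe malaria. They are not to be treated or reported as AEs and go in their own part of the CRF.
- Protocol 8.2 nevertheless refers to SAEs, including deaths, that result from deterioration of severe malaria, and has them reported monthly instead of within 24 hours.
- SAP 3.5, Table 5, has a row "Possible, probable or definite drug related SAEs, n/N", compared by arm with a p-value. The same table counts severe-malaria conditions as graded adverse events.

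**The concern.** A causality scale should become harder to satisfy as it rises. Here the highest level is easier to reach than the one below it. The lowest level is worded so that closeness to a dose appears to rule it out.

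That matters in this population. Appendix 1 gives injections at 0, 12 and 24 hours, and Appendix 4 says most deaths from severe malaria occur within 24 hours of admission. Early serious events will therefore often follow a dose closely, whatever their cause. In an open-label trial at two sites, a rule that lets the same event be rated at either end of the scale makes the drug-related SAE comparison hard to interpret. The rating also has a use outside the tables: Protocol 12.7 commits the study to paying for treatment of drug-related SAEs.

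**Working it through.** The plan gives no figure on this point, so the check is one of wording.

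**Step 1: the four definitions against all event profiles.** Take timing (clear, less clear, none), improvement on withdrawal (yes, no) and another cause (yes, no): 3 × 2 × 2 = 12 profiles. The two parts of Not related are joined only by a semicolon, so it is read both ways.

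| Timing | Improves on withdrawal | Another cause | Profiles | Fits, if Not related needs both parts | Fits, if either part is enough |
|---|---|---|---|---|---|
| Clear | yes | no | 1 | Definite, Probable | Definite, Probable |
| Clear | no | no | 1 | Definite | Definite |
| Clear | yes or no | yes | 2 | Definite | Definite, Not related |
| Less clear | yes or no | yes | 2 | Possible | Possible, Not related |
| Less clear | yes or no | no | 2 | none | none |
| None | yes or no | yes | 2 | Not related | Not related |
| None | yes or no | no | 2 | none | Not related |

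**Step 2: order.** All 4 clear-timing profiles meet Definite, and only 1 of those 4 meets Probable. Probable is a strict subset of Definite, so the order is inverted.

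**Step 3: lower boundary.** In the 2 profiles with clear timing and another cause such as malaria, Definite is the only literal fit on the stricter reading. On the looser reading both Definite and Not related fit, and nothing says which to choose.

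**Step 4: gaps.** Less clear timing with no other cause fits nowhere, if both parts of Possible are required. Reading that semicolon as an alternative closes the gap, but then clear timing with another cause also fits Possible, which is still inside the pooled row.

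**Step 5: effect on Table 5.** The row counts Possible + Probable + Definite. Moving an event between Definite and Probable leaves that sum unchanged. Moving it between Definite and Not related changes it by one. Only the Not related boundary affects the row.

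**Step 6: which malaria events reach the scale.** Under 8.1.2 an SAE is a kind of AE. Under 8.1.1 listed malaria deterioration is not an AE. Under 8.2 there are SAEs from malaria deterioration, and under 8.3.3 every AE and SAE is rated. Table 5 has 13 symptom rows. Nine correspond broadly to conditions on the 8.1.1 list: coma, convulsions, respiratory distress, shock, jaundice, haemoglobinuria, renal failure, bleeding and severe anaemia. Four do not: prostration, failure to feed, suspected pulmonary oedema and repeated vomiting. SAP 3.5 limits the summaries to events that start or worsen after dosing, which for the nine is what 8.1.1 takes out of AE reporting.

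**The case against.** A reader might infer that malaria complications in general will be scored as drug related, so that the Table 5 row would mostly count malaria. The documents do not support that.

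- Section 8.1.1 keeps the main complications away from the scale. This stands for the 13 listed conditions. It does not cover unlisted ones, and 8.2 keeps SAEs and deaths from deterioration in play.
- Not related names the patient's known clinical state, and 8.2 already expects investigators to attribute some events to malaria. A sensible investigator may well choose Not related. This stands: the defect is ambiguity, with misclassification possible but not certain.
- Putting a percentage on the contamination would need rates of malaria-driven and drug-related SAEs that the documents do not give, and a time window for association that they do not define.
- The row could not detect a rare reaction under any wording. Section 12.4.1 puts severe allergy at about 1 in 3000, so 100/3000 ≈ 0.03 cases are expected per arm of 100. This stands for the comparison, but each case still needs a defensible rating.
- The AE comparison is exploratory in the protocol (SAP 2.1.3 lists it as secondary), is not powered, and is largely descriptive. SAE reporting in 8.2 does not turn on the relatedness grade. Both points stand and limit the importance.
- The Definite line alone lacks a closing full stop and stands before a break in the text, so words may have been lost. If the approved protocol or the AE/SAE form says more, the inversion could disappear; the Not related problem would remain.

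Section 12.4.1 also says of nausea, vomiting, anorexia and diarrhoea that "it is uncertain whether these are attributable to the drug or to the disease severe malaria". That concerns minor symptoms and is not evidence about SAEs, though it shows why the lower boundary needs clear wording.

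**Conclusion.** The point holds in a limited form. As printed, Definite asks for less than Probable, and Not related can be read as unavailable for any event that closely follows a dose. An unlisted malaria-related AE, or an SAE or death from malaria deterioration, can then be rated Definite; if serious, it can be counted in the drug-related SAE row. The inversion by itself does not alter that row; the Not related boundary does.

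No numerical size can be given from the documents. The reach is the drug-related SAE row of Table 5 and the individual ratings behind it. Preparation time, cost and the sample size are unaffected. The conclusion assumes that the printed Definite line is complete and that the AE/SAE form carries no fuller definitions. It merits correction because the new formulation has, by the protocol's own account (3.2), not yet been deployed in severe malaria patients.

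**What to change.** 1. Definite: clear timing, not reasonably explained by the clinical state or another aetiology, plus supporting evidence such as a recognised immediate reaction.
2. Not related: the clinical state or another cause explains the event, whatever the timing.
3. Possible: extend it to less clear timing with no other aetiology identified.
4. Test the revised key against the twelve profiles so that each has one home. Clear timing with no other explanation and no information on withdrawal needs attention: a fatal event cannot show improvement, so it can never meet Probable as now worded.
5. Table 5: report definite and probable together, and possible in a separate row.
6. Reconcile Protocol 8.1.1 and 8.2 with SAP Table 5. State whether malaria-deterioration events are AEs or SAEs, whether they are rated for relatedness, and which CRF section feeds the symptom rows.

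The cost is protocol and SAP wording, a revised key on the AE/SAE form, one extra table row and brief site retraining. No new data items are needed. Any events already rated under the present key would need re-rating from the recorded narrative.

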8.3.4. Outcome

The investigator will follow-up the AE and SAE until resolution, death, deemed permanent and no further medically relevant information can be expected. AE and SAE outcome will be classified as follows:

- Continuing/ongoing
- Resolved
- Resolved with sequelae
- Permanent
- Fatal

9. STATISTICAL CONSIDERATIONS

9.1. Sample size justification

Part 1:

Sample size calculations for non-inferiority study is based on dissolution test data from Guilin Pharmaceutical Co. Ltd. ("Study report on the solubility of artesunate for injection (60mg), Doc. RR-QC-ZSYQHHZ (60mg)RJX-2021 30th April 2021).²³ This is supported by unpublished in-house experience (from a bioequivalence study in healthy volunteers, personal communication, [name], Mahidol University) that the conventional formulation takes about 4 minutes with a standard deviation of 2 minutes to administer injectable artesunate. Our non-inferiority margin is 1 minute of drug re-constitution for the new simpler artesunate formulation i.e. if participants in the 1-step artesunate formulation will have a mean of the time of 5 minutes or less of drug re-constitution, with a standard deviation of 2 minutes, then the new formulation will be considered to be non-inferior to the old formulation. With this non-inferiority margin, detecting non-inferiority with 90% power and with a one sided alpha of 0.025, we will need to recruit 85 participants in the new formulation and 85 in the old formulation arm giving a total of 170 participants. In order to compensate for a 15% loss to follow-up or withdrawal, we will need 100 participants in each arm giving a total of 200 participants in the two arms combined. These calculations were performed in Stata 16 (StataCorp LLC Software).

The sample size calculation dovetails with pragmatic needs for the other study activities the 200 participants provides sufficient variability of participant characteristics to allow staff to gain experience of using 1-step artesunate and be able to provide an informed opinion of its pros and cons. Recruitment of 100 patients per site is feasible over 12 months based on the expected numbers of cases of severe malaria ([name] and [name], personal communication April 2021). The sample size calculation is based only on the time-to-treatment of participants and not on the costing analysis.

Part 2:

Number of respondents (sample size) for this study will be based on the principles of 'data saturation', that is data are collected until no new data/themes emerge from further interviews. A minimum of 40 respondents in total will be recruited for the SSIs, and at least 150 health workers will be interviewed with the survey questionnaire.

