2. GENERAL ANALYSIS APPROACH

The principle of intention to treat (ITT) will be the main strategy of analysis for the primary outcome. These analyses will be conducted on all patients assigned to the treatment groups as randomised. Any patients subsequently found not to be eligible during the trial or that did not receive a full course of study drug will be included in these analyses. Per Protocol (PP) analysis will be conducted to examine robustness of ITT results. This will be a form of sensitivity analysis to the intention to treatment analysis principle. In the PP analyses, all patients wrongly included in the study based on the inclusion/exclusion criteria will be excluded from analyses.

The cost analysis of 1-step parenteral AS will assess health facility-level costs, and health system costs to encompass all costs of a potential change from conventional to 1-step artesunate, including re-training, materials, drug replacement. Unit costs will be assigned to healthcare worker time spent on managing patients with severe malaria (derived from the time and motion surveys). Micro costing will be carried out in each of the sites to estimate the costs of equipment and consumables associated with provision of artesunate with each of the formulations. The resulting labour and consumable mean costs will be compared in patients treated with 1-step vs conventional artesunate formulation.

Time from opening box to completed preparation of syringe will be summarised using means and standard deviation for each each arm. Difference in means and the correponding 95% confidence intervals will be reported. We will provide overall comparisons by arm as well as for each site separately. The comparisons will be done for baseline times ans well as for all recorded times. Total cost of consumables in US dollars will be summarised in a similar way. A Student's independent t-test will be used for comparison of means between groups. The Central Limit Theorem justifies the use of the Student's t-test even if the times/costs may not be normally distributed because of the large sample size. However, if the data will be highly skewed, non-parametric tests such as Manny-Whitney (Wilcoxon) U test will be considered. Statistical significance will be declared at 5% significance level.

Data analysis will be performed using Stata 17 or higher, StataCorp, 4905 Lakeway Drive College Station, Texas 77845 USA

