2.2.1 Determination of sample size

Sample size calculations for non-inferiority study is based on dissolution test data from Guilin Pharmaceutical Co. Ltd. ("Study report on the solubility of artesunate for injection (60mg), Doc. RR-QC-ZSYQHHZ (60mg)RJX-2021 30th April 2021).²³ This is supported by unpublished in-house experience (from a bioequivalence study in healthy volunteers, personal communication, [name], Mahidol University) that the conventional formulation takes about 4 minutes with a standard deviation of 2 minutes to administer injectable artesunate. Our non-inferiority margin is 1 minute of drug re-constitution for the new simpler artesunate formulation i.e. if participants in the 1-step artesunate formulation will have a mean of the time of 5 minutes or less of drug re-constitution, with a standard deviation of 2 minutes, then the new formulation will be considered to be non-inferior to the old formulation. With this non-inferiority margin, detecting non-inferiority with 90% power and with a one-sided alpha of 0.025, we will need to recruit 85 participants in the new formulation and 85 in the old formulation arm giving a total of 170 participants. In order to compensate for a 15% loss to follow-up or withdrawal, we will need 100 participants in each arm giving a total of 200 participants in the two arms combined. These calculations were performed in Stata 16 (StataCorp LLC Software).

The sample size calculation dovetails with pragmatic needs for the other study activities the 200 participants provides sufficient variability of participant characteristics to allow staff to gain experience of using 1-step artesunate and be able to provide an informed opinion of its pros and cons. Recruitment of 100 patients per site is feasible over 12 months based on the expected numbers of cases of severe malaria ([name] and [name], personal communication April 2021). The sample size calculation is based only on the time-to-treatment of participants and not on the costing analysis.

STATISTICAL ANALYSIS PLAN

3. Data Analysis

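### The trial is sized on a 1-minute non-inferiority margin, but its only written criterion is a 1-step mean of 5 minutes or less, and the planned 95% CI is never compared with the margin

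*Protocol*

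**What the plan says.** The Synopsis describes a non-inferiority trial. Protocol 9.1, repeated in SAP 2.2.1, states: "Our non-inferiority margin is 1 minute of drug re-constitution for the new simpler artesunate formulation". It then restates the margin as a condition, "if participants in the 1-step artesunate formulation will have a mean of the time of 5 minutes or less of drug re-constitution", with an SD of 2 minutes, and gives the consequence: "then the new formulation will be considered to be non-inferior to the old formulation". The following sentence sets the operating characteristics: "With this non-inferiority margin, detecting non-inferiority with 90% power and with a one sided alpha of 0.025".

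The analysis text does not return to the margin:

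- SAP section 2 says "Difference in means and the correponding 95% confidence intervals will be reported". It adds that a Student's "independent t-test will be used for comparison of means between groups", that "if the data will be highly skewed, non-parametric tests such as Manny-Whitney (Wilcoxon) U test will be considered", and "Statistical significance will be declared at 5% significance level".
- SAP Table 2 has columns for the difference, its 95% CI and a p-value, for baseline times and for all recorded times. It has no margin and no non-inferiority conclusion.
- Protocol 9.2 compares median times. Protocol 9.2.3 allows means with 95% CIs and lists t or rank tests.
- Protocol 9.2.1 makes ITT the main analysis and per-protocol the sensitivity analysis.

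**The concern.** Preparation time is co-primary endpoint 1 and the only endpoint on which the trial is sized, so its decision rule has to be written down and has to carry the stated error rate. The 5-minute sentence can be read in two ways, and neither gives such a rule.

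- **Literal reading.** 1-step is non-inferior if its own observed mean is at most 5 minutes. There is no confidence limit, and the observed 2-step mean plays no part.
- **Gloss reading.** The 5 minutes merely illustrates planning mean 4 plus margin 1. Then nothing says how non-inferiority is concluded. The only inference attached to the time data is a test of no difference, and a non-significant result from that test does not show non-inferiority.

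On the first reading, a report could declare non-inferiority beside a p-value showing 1-step significantly slower. On the second, the analysts of an open-label trial would have to settle the rule after seeing the times.

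**Working it through.** **Inputs** (Protocol 9.1, SAP 2.2.1): 2-step mean 4 minutes, SD 2, margin 1 minute, one-sided alpha 0.025, power 90%, 85 per arm, 15% loss, 100 per arm. A true difference of 0 is not stated, but it is the value that reproduces 85. Times are treated as independent.

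**1. The plan's own figure.** n = 2(z₀.₉₇₅ + z₀.₉₀)²σ²/Δ² = 2 × (1.960 + 1.2816)² × 2²/1² = 84.06, so 85 per arm. Then 85/0.85 = 100. Both reproduce, using a two-arm test of the difference against the margin.

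**2. Literal 5-minute rule.** P(pass) = Φ((5 − μ₁)/(2/√n)), where μ₁ is the true 1-step mean. The standard error of one mean is 0.217 (n = 85) or 0.200 (n = 100).

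The documents give only a 2-step mean of 4. The other 2-step means below are assumptions to show sensitivity.

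| True 2-step mean | True 1-step mean | Pass, n = 85 | Pass, n = 100 |
|---|---|---|---|
| 4 | 5 (at the margin) | 50% | 50% |
| 3.5 | 4.5 (at the margin) | 98.9% | 99.4% |
| 4.5 | 5.5 (at the margin) | 1.1% | 0.6% |
| 5.5 | 5.5 (identical) | 1.1% | 0.6% |

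The first three rows should all read 2.5%. The last should be about 90% or more.

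**3. Conflict with the SAP's own test.** The SE of the difference is 2√(2/n) = 0.307 (n = 85) or 0.283 (n = 100), and the 95% half-width (t) is 0.606 or 0.558. Observed means of 5 and 4 meet the 5-minute rule, yet the CI is 0.39 to 1.61 (n = 85) or 0.44 to 1.56 (n = 100). That interval excludes 0 and extends past the margin. In 1,000,000 simulated trials with true means 5 and 4, the rule was met while the t-test showed 1-step significantly slower in 40.5% (n = 85) and 44.2% (n = 100).

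**4. Gloss reading, planning case (both means 4).** The two-sided 5% t-test is non-significant in 95% of trials and gives no non-inferiority conclusion.

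**5. The planned CI compared with 1 minute** (non-central t).

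- True difference 1: passes 2.5%, as stated.
- True difference 0: passes 90.0% (n = 85) or 94.0% (n = 100).
- Largest passing observed difference: 1 − 0.606 = 0.394 or 1 − 0.558 = 0.442 minutes, at SD 2.

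**6. When 1-step is faster** (assumed 3 against 4): both rules pass in more than 99.9%.

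**7. Skewed times** (assumed lognormal, means 5 and 4, 2-step SD 2, 1-step SD 2 to 2.5; 200,000 trials each): the t-based CI rule has 2.4% to 2.8% error at the margin. The 5-minute rule passes 51%, and the conflict in step 3 occurs in 36% to 45%.

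**The case against.** The strongest reply is that the literal reading is not what was meant. The sentence opens by explaining the margin, and the next one gives a one-sided alpha and a power. A cut-off on one arm's mean has no alpha and would not need 85 children in the other arm. Since a one-sided 0.025 test against 1 minute is the same as checking the upper limit of the planned 95% CI, all the components are already in the plan and only the linking sentence is missing. This is a fair account of the probable intent, and the components are indeed there. But a sample-size input is not a decision rule: the one condition that is written contradicts the intended one, and SAP section 2 attaches a different inference to the interval.

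Second, being significantly slower and being non-inferior can both hold, when the CI lies between 0 and 1. That is true, but only if the observed SD is below about 1.65 (85 per arm) or 1.79 (100 per arm), not at the planned SD of 2. The conflict rate shows how the report would look; the 50% is the error rate.

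Third, both documents expect 1-step to be faster, and then the rules agree. This limits the scope. Similar times remain plausible, however: Appendix 1 gives up to 3 to 5 minutes of shaking for 1-step, and Protocol 3.1 gives 3 to 5 minutes for 2-step.

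Fourth, naming the baseline dose and keeping the mean difference under skew go beyond the missing sentence. They do, but they follow from a margin and a sample size set on one mean time per child.

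**Conclusion.** The concern holds, and the text is wrong as written. The sample size and the planned estimate are sound; the fault is in the decision rule. Read literally, the rule has a 50% false-positive rate at the planning 2-step mean of 4, and between about 1% and 99% for 2-step means of 4.5 down to 3.5, against the stated 2.5%. Read as a gloss, no planned inference can conclude non-inferiority, although the planned CI set against 1 minute would do so in 90.0% to 94.0% of trials when the arms are equal.

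This matters if preparation times are similar or 1-step is slower. If 1-step is clearly faster and well below 5 minutes, the conclusion is the same under either rule.

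The figures assume SD 2 (apart from the skew check) and independent times. The number of nurses is not given. If one nurse prepares doses for several children, times may be correlated, which these figures do not cover.

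**What to change.** In Protocol 9.1 and SAP 2.2.1, replace the 5-minute phrase with:

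> The margin is a difference of 1 minute in mean preparation time (1-step minus 2-step). Planning values are 4 minutes in both arms, SD 2.

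In SAP section 2 and under Table 2, add:

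> 1-step is non-inferior if the upper limit of the two-sided 95% CI for the difference in mean preparation time (1-step minus 2-step, baseline dose, ITT, with per-protocol as sensitivity analysis) is below 1 minute. If so, it is faster if that limit is also below 0.

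The baseline dose gives one time per child, which matches the sample-size unit; the comparison of all recorded times stays as planned. Keep the mean-difference CI as the basis for the decision even if times are skewed, because the margin is defined on means. Treat the medians in Protocol 9.2 and the Mann-Whitney test as supportive.

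The cost is wording in two documents, with whatever approval Protocol 12.3 requires if the sponsor regards it as a substantial amendment. N, data collection and the list of analyses do not change.
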